5.3. Major Secondary Endpoints

The major secondary efficacy endpoint is progression-free survival (PFS).

5.3.1. Definition

PFS, defined as the duration from the date of randomization to either PD or death, whichever occurs first. Disease progression will be determined according to IMWG 2016 criteria per computer algorithm. For subjects who have not progressed and are alive, data will be censored at the last disease evaluation before the start of any subsequent anti-myeloma therapy. Subjects who withdrew consent from the study before disease progression will be censored at the last disease assessment. Subjects who are lost to follow-up will be censored at the last disease and are still alive at the cutoff date for analysis will be censored at the last disease assessment. Subjects without any post-baseline disease assessment will be censored at the date of randomization.

Situation	Outcome	Date of Event or Censoring
Disease progression prior to start of subsequent antimyeloma therapy	PFS event	Earliest date that indicates disease progression
Death without subsequent antimyeloma therapy and without disease progression *	PFS event	Date of death
No postbaseline disease assessment after randomization	Censored	Date of randomization
Disease progression or death immediately after 2 or more missing consecutive disease evaluations	Censored	Date of last disease assessment
 Others, such as: Withdrawal of consent to study participation Lost to follow-up Start of subsequent antimyeloma therapy prior to disease progression or death 	Censored	Date of last disease assessment prior to withdrawal of consent to study participation, lost to follow-up, or start of subsequent antimyeloma therapy

Table 4	· PFS	Event and	Censoring	Method
1 and 4	• 1 1 0		CCHSUI III2	INTERIOU

*Subjects who died after consent withdrawal will be censored at the date of consent withdrawal from PFS analysis

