5.4.1. Definition

MRD by NGS are evaluated post-baseline at the end of 12, 18, 24, and 36 months after the start of study treatment(s). The overall MRD negativity (10^{-5}) conversion rate at any time after randomization is defined as the rate of MRD converted from positive at baseline to negativity at the threshold 10^{-5} achieved at any time after randomization.

In addition, MRD negativity (10^{-5}) conversion rate at 12, 18, 24 and 36-months landmark time with +/- 2 months window, as well as accumulative rate up to these timepoints will be summarized. MRD negativity (10^{-5}) CR conversion rates for FAS patients, and MRD negativity (10^{-5}) conversion rates for those achieved CR or better response per computerized algorithm will be summarized in a similar manner.

Durable MRD (≥ 1 year) negativity rate, defined as the proportion of subjects who have achieved MRD negative status (at 10⁻⁵) in 2 bone marrow aspirate examinations that are a minimum of 1 year apart, without any examination showing MRD positive status in between assessments. Subjects who have achieved MRD negative status on or after PD or switch to subsequent antimyeloma therapy before PD, will not be considered MRD negative. Subjects with missing or unevaluable MRD status will be considered as MRD positive.

Similar analysis will be performed for durable MRD (≥6 months) negativity rate.

OS, measured from the date of randomization to the date of the subject's death due to any cause. Subjects who died after consent withdrawal will be considered as having an OS event. Subjects who are lost to follow-up will be censored at the time of lost to follow-up. If the patient is alive and vital status is unknown, then the patient's data will be censored at the date the patient was last known to be alive determined by the maximum collection/assessment date from among selected data domains within the clinical database.

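### SAP 5.3.1 gives conflicting PFS rules: a death with no post-baseline assessment is both an event and censored at day 0, and a consent withdrawer's censoring date depends on a later death

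*SAP*

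**What the plan says.** SAP 5.3.1 defines the endpoint as "PFS, defined as the duration from the date of randomization to either PD or death, whichever occurs first". Text and Table 4 then set the event and censoring rules.

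- **Death.** Table 4 lists "Death without subsequent antimyeloma therapy and without disease progression" as a PFS event on the date of death. It does not require an earlier disease assessment.
- **No assessment.** The next row, "No postbaseline disease assessment after randomization", is censored at randomization. The text repeats it: "Subjects without any post-baseline disease assessment will be censored at the date of randomization". Neither mentions death.
- **Consent withdrawal.** The text says "Subjects who withdrew consent from the study before disease progression will be censored at the last disease assessment". The 'Others' row of Table 4 agrees: "Date of last disease assessment prior to withdrawal of consent to study participation, lost to follow-up, or start of subsequent antimyeloma therapy".
- **Footnote to the death row.** "Subjects who died after consent withdrawal will be censored at the date of consent withdrawal from PFS analysis".

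SAP 5.1.2 (data handling) and SAP 5.3.2 (PFS methods, sensitivity and supplementary analyses) state no precedence among these rules. SAP 5.1.1 makes PFS the key secondary endpoint, tested hierarchically after the primary endpoint, with an O'Brien-Fleming interim look.

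**The concern.** The first conflict changes the outcome itself. Applied literally, the no-assessment rule removes a true event from the only alpha-controlled secondary endpoint and contributes zero follow-up time in its place. Whether that happens is left to whoever programs the derivation, in an open-label trial where early dropout could differ by arm.

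The second conflict changes only a date, since the patient is censored either way. But under the footnote two patients with identical histories up to withdrawal get different censoring times because one is later known to have died. Only the one who died is credited with event-free time in which progression was not being assessed.

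**Working it through.** **Can the overlap occur?** SAP 2.6 defines baseline as the closest value on or before first dose. Protocol 9.3.1 places disease evaluations before dosing. The Time and Events Schedule runs C1D1, C3D1, C6D1 and so on. C1D1 can therefore be baseline and C3D1 the first post-baseline visit, 2 × 28 = 56 days after first dose. Randomization may precede first dose by up to 3 business days, so the window from randomization is about 56 to 61 days. PFS uses all randomized patients (SAP 2.3.1, 5.3.2), so a patient randomized but never assessed who dies later is also caught.

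**Reproducing the plan's figures.** Inputs from SAP 1.4: HR 0.50, medians 60 and 120 months, 107 per arm, 12-month accrual, 36 months after the last patient, two-sided alpha 0.05.

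- Schoenfeld power = Φ(√d/2 × ln 2 − 1.96). For d = 64: Φ(2.773 − 1.960) = 79.2%. The plan states about 79%.
- Expected events per arm, exponential PFS, uniform accrual, no dropout: 107 × {1 − [exp(−36λ) − exp(−48λ)]/(12λ)}, with λ = ln 2/median. Lenalidomide 41.1, combination 23.0, total 64.1. The plan states 64.

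**Size of conflict (a).** Expected PFS events of any kind before C3D1 = 107 × [1 − exp(−λt)] in each arm.

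| Window | Lenalidomide | Combination | Total |
|---|---|---|---|
| 56 days (1.84 months) | 2.25 | 1.13 | 3.4 |
| 61 days (2.00 months) | 2.45 | 1.23 | 3.7 |

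Deaths are a subset of these. If every one were lost, about 60 events would remain.

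| Events | 64 | 63 | 62 | 61 | 60 |
|---|---|---|---|---|---|
| Power | 79.2% | 78.5% | 77.9% | 77.2% | 76.6% |

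The largest loss shown is 79.2 − 76.6 = 2.6 points. Allowing for the interim look (final nominal level about 0.049) gives 78.9% and 76.3%, much the same loss. At the PFS interim, planned at about 32 events, each reclassified event is 1/32, or about 3%, of the information.

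**Size of conflict (b).** The two dates differ by the time since the last disease assessment.

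- In years 2 and 3, M-protein and IMWG response visits fall every sixth cycle: 6 × 28 = 168 days.
- Serum FLC continues every third cycle: 3 × 28 = 84 days. A sensitivity analysis in SAP 5.3.2 counts FLC among the scheduled disease evaluations.

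The scheduled on-treatment gap is therefore about 84 days if FLC visits count and up to about 168 days if they do not. The event count does not change.

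**The case against.** The best defence of (a) is that the sense is clear. PFS includes death by definition. Protocol 2.1 (Table 1) and SAP 5.3.1 both introduce censoring for patients who are alive and progression-free, and the death row stands first in Table 4. On that reading the no-assessment rule simply elaborates the rule for the living. This is the likelier intent and it supports the fix, but it does not settle the wording: the row and the sentence are unqualified, although the authors attached an explicit exception to the death row by asterisk. SAP 5.3.2 requires censoring reasons to be tabulated, which would expose day-0 censoring but not prevent it. Its sensitivity analysis for events after two or more missed evaluations does not help either, because a patient who dies before C3D1 has missed none.

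For (b), the footnote can be read as a deliberate special case overriding a general rule. That is fair, and it would remove the contradiction. It would leave a censoring date that depends on a later death, with no reason given.

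Two stronger inferences are tempting, and the documents support neither.

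- *That the hazard ratio would move materially.* This needs early deaths concentrated in one arm, and the documents give no early-death rate. If losses followed the planned proportions, the event ratio would change by (21.9/38.8)/(23.0/41.1) ≈ 1.01.
- *That overall survival has the same fault.* SAP 5.4.1 says "Subjects who are lost to follow-up will be censored at the time of lost to follow-up", a date it does not define. But its next sentence keeps the date last known alive where vital status is unknown, and SAP 5.1.1 makes OS exploratory.

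**Conclusion.** Both conflicts are in the current text. Conflict (a) is a wrong rule as written, since one of two unqualified rules erases a death from an endpoint that includes death. Conflict (b) concerns only a date, but the date should not depend on what happens after censoring.

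The expected effect is small: at worst about 60 events and 76.6% power instead of 64 and 79.2%. That rests on exponential PFS at the planned medians, no dropout, and the loss of every PFS event expected before C3D1, progressions included. It is an expectation, so the observed number could be higher, and it does not cover later deaths in never-assessed patients. The number of patients who withdraw consent and are then known to have died cannot be estimated from the documents. The case for correcting the text rests on the status of PFS and the ease of the change, not on a large predicted bias.

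**What to change.** In SAP 5.3.1 and Table 4:

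1. Change the no-assessment row and sentence to *no post-baseline disease assessment and not known to have died*.
2. State that a death without subsequent antimyeloma therapy before the first scheduled assessment is a PFS event on the date of death.
3. State which rule governs a never-assessed patient who dies after two or more missed evaluations. That patient meets both the death row and the missed-evaluations row, and the latter's censoring date would have no post-baseline assessment to refer to.
4. Change the footnote so that all consent withdrawers, whether or not they later die, are censored at the last disease assessment before withdrawal.

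The cost is SAP wording and a few lines of derivation code, settled before PFS is analysed. No new data or patients are needed, and the design stays at 64 events and 79.2% power.

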5.3.2. Analysis Methods

Analysis of PFS will be based on the FAS. The Kaplan-Meier method will be used to estimate the distribution of overall PFS for each treatment group. The median PFS with 95% CI will be provided. In addition, the number and percentage of subjects who had a PFS event or were censored will be reported. The reasons for PFS censoring will be summarized accordingly. The Kaplan-Meier PFS curve will also be plotted by treatment group.

The treatment comparison of the distribution of overall PFS will be based on a stratified log-rank test. The p-value from a stratified log-rank test will be reported. Hazard ratio and its 95% confidence interval will be estimated based on a stratified Cox's regression model with treatment

as the sole explanatory variable. Stratification factor used in the analyses include baseline cytogenetic risk (high risk versus standard/unknown risk) as used for randomization of the study.

In addition, PFS rate with 95% CI will be estimated at various time points by Kaplan-Meier method for each treatment group.

To evaluate the robustness of PFS analysis, the following sensitivity and supplementary analyses may be performed in a similar manner as described above:

Sensitivity

- Unstratified analysis of PFS by using unstratified log-rank test and unstratified Cox's regression model
- Progressive disease based on investigator assessment according to the IMWG response criteria
- Not censoring for death or disease progression after 2 or more missing consecutive disease evaluations: For any disease progression identified by the computer algorithm or death, if there are 2 or more consecutive missing scheduled disease evaluations between the event date and the latest date of scheduled disease evaluation (includes serum M-protein, urine M-protein, and serum FLC only) immediately preceding the event, this event will be considered as a PFS event in the analysis

Supplementary

- Not censor the events after the start of subsequent antimyeloma therapies; Progression or death occurred after the start of subsequent anti-myeloma therapies will NOT be censored at the last disease assessment before the start of subsequent therapies. If there is no confirmed progressive disease, the subjects will be censored at the last disease assessment before subjects are lost to follow-up or withdrawal of consent to study
- Censor the death due to COVID-19 at the date of last disease evaluation before the date of death for those who have not developed a confirmed PD
- Censor the subjects who permanently discontinue treatment/study due to COVID-19 (censor at last disease evaluation before treatment/study discontinuation)
- PFS subgroup analysis by overall MRD conversion status (at 10⁻⁵) for subjects who achieved MRD (at 10⁻⁵) conversion from positive at baseline to negative at any time during treatment period, and for subjects who did not achieve the MRD negative conversion.
- PFS subgroup analysis according to Section 2.4. Analysis will be performed similarly as the main PFS analysis except that randomization stratification factor will be excluded from Cox model and log-rank test. Forest plot will be generated.

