5.2.1. Definition

The primary endpoint of this study is the MRD conversion rate from baseline to 12 months after start of maintenance treatment. It is defined as the proportion of subjects who were MRD [at 10⁻⁵] positive at baseline and have achieved MRD negative status [at 10⁻⁵] as determined by NGS by 12 months of maintenance treatment. The primary endpoint will be analyzed based on FAS.

Subjects' MRD positive status at baseline should be verified. Since subjects do not always adhere to the protocol visit schedule, the post-baseline MRD records from randomization up to 12-month + 2 months will be selected for MRD negativity status evaluation. Subjects with missing or unevaluable MRD status will be considered as MRD positive. Subjects who have achieved MRD negative status on or after PD or switch to subsequent anti-myeloma therapy before PD, will not be considered MRD negative in the primary endpoint analysis.

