5.4.2. Analysis Methods

The analysis of the overall MRD (10^{-5}) conversion rate at any time after randomization, durable MRD negativity rate, the CR or better rate, and sCR rate will be performed similarly to that for the primary endpoint on the FAS, as described in Section 5.2.3. Similarly, for thresholds 10^{-4} and 10^{-6} , the overall MRD negativity rate at any time after randomization will be analyzed similarly as for the threshold 10^{-5} .

The time-to-event variables (ie., OS, duration of CR, PFS2 and time to subsequent antimyeloma therapy) will be performed using the approach for PFS, as described in Section 5.3.2.

Time to the first response of CR or better will be summarized using descriptive statistics for those who reached CR or better response.

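### The optional PFS analysis by MRD conversion (SAP 5.3.2) does not state its contrast; DR vs R within groups is not randomised, and converters vs non-converters carries immortal-time bias

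*SAP*

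**What the plan says.** SAP 5.3.2 ends with a list introduced by "the following sensitivity and supplementary analyses may be performed in a similar manner as described above". One supplementary item is a "PFS subgroup analysis by overall MRD conversion status" at the 10⁻⁵ threshold, covering patients with "conversion from positive at baseline to negative at any time during treatment period, and for subjects who did not achieve the MRD negative conversion".

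The method above that list is the DR vs R stratified log-rank test and a stratified Cox model with treatment "as the sole explanatory variable". The same section adds Kaplan-Meier curves, and "PFS rate with 95% CI will be estimated at various time points by Kaplan-Meier method for each treatment group". The time origin is in SAP 5.3.1: "PFS, defined as the duration from the date of randomization to either PD or death".

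Scheduled post-baseline MRD samples are at C13D1, C19D1, C25D1 and the end-of-treatment visit (Protocol, Time and Events Schedule Part 1). An aspirate is also requested at progression where feasible (Part 2). Treatment stops at confirmed progression.

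For the primary endpoint, SAP 5.2.1 does not count as negative "Subjects who have achieved MRD negative status on or after PD or switch to subsequent anti-myeloma therapy before PD". The supplementary PFS item does not repeat that rule. For the overall conversion rate, SAP 5.4.2 says the analysis "will be performed similarly to that for the primary endpoint on the FAS, as described in Section 5.2.3", which is the methods section and not the definition in 5.2.1. SAP 5.4.1 uses the word landmark only for MRD rates; no landmark or time-dependent method is given for PFS.

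**The concern.** The item can be read in two ways, and each has a fault.

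- **DR vs R within converters and within non-converters.** Conversion is measured after randomisation, and the trial expects treatment to change it (20% vs 40%). Patients within a conversion group are no longer comparable by randomisation, and nothing in the SAP says so. A within-group hazard ratio could be taken for a randomised result.
- **Converters beside non-converters.** To be a converter, a patient must normally stay event-free until a sample is taken. That guaranteed event-free time is credited to converters, while early progressions and deaths go to non-converters. Curves or a hazard ratio from randomisation would then suggest that conversion predicts PFS even if it did not. The protocol's rationale (3.2.4) rests on MRD-negative patients having longer PFS, so readers are likely to make this comparison. The literal reading also invites it, because it produces Kaplan-Meier curves for each group.

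**Working it through.** **Inputs.** From SAP 1.4: 107 patients per arm; median PFS 60 months (R) and 120 months (DR); 1 year of accrual; follow-up to 36 months after the last randomisation; conversion of 20% (R) and 40% (DR) by month 12. From the schedule, with 28-day cycles: C13D1 = 12 × 28 = day 336 (11.04 months), C19D1 = day 504, C25D1 = day 672, and end of treatment about 36 × 28 + 30 = day 1038. PFS is taken as exponential, λ = ln 2 / median, without dropout.

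**Reproducing the plan's PFS figures.** Expected events per arm = 107 × [1 − (e^(−36λ) − e^(−48λ)) / (12λ)].
- R: 107 × 0.3839 = 41.1. DR: 107 × 0.2153 = 23.0. Total 64.1, against the planned 64.
- Power (Schoenfeld) = Φ(√64 × ln 2 / 2 − 1.96) = Φ(0.81) = 79.2%, against about 79%.

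**Events before the first scheduled sample.** S(11.04) is 0.8803 on R and 0.9382 on DR. Expected events before day 336 = 107 × 0.1197 + 107 × 0.0618 = 19.4, about 30% of 64.1. If first samples came at month 10, 17.7 events (28%) would still precede them.

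**Closed form, conversion unrelated to PFS, none after day 336.** Let p be the conversion probability among sampled patients, set so that 20% / 40% of all randomised patients convert: p = 0.20 / 0.8803 = 22.7% (R) and 0.40 / 0.9382 = 42.6% (DR). Month-36 PFS from randomisation is then:
- converters: S(36) / S(11.04);
- non-converters: S(36)(1 − p) / (1 − p·S(11.04)).

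| Arm | All patients | Converters | Non-converters |
|---|---|---|---|
| R | 66.0% | 0.6598 / 0.8803 = 74.9% | 0.6598 × 0.773 / 0.80 = 63.7% |
| DR | 81.2% | 0.8123 / 0.9382 = 86.6% | 0.8123 × 0.574 / 0.60 = 77.7% |

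The gaps of about 11 and 9 percentage points arise from immortal time alone.

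**Simulation, converters vs non-converters.** 2,000 trials per scenario, follow-up uniform over 36 to 48 months, MRD sampled at the four times above in patients still event-free, conversion independent of PFS, Cox models adjusted for arm, median hazard ratios. Conversion rates after month 12 are not in the documents, so a range is assumed.

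| Assumed conversion per later visit | Ever/never HR (nominally significant) | Time-dependent HR | 14-month landmark HR |
|---|---|---|---|
| 0% | 0.62 (31%) | 0.99 | 0.99 |
| 5% | 0.51 (64%) | 0.99 | 1.00 |
| 10% | 0.43 (88%) | 0.99 | 0.99 |
| 15% | 0.37 (96%) | 1.00 | 1.01 |

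The two corrected methods reject in 4 to 5% of trials. If 20% / 40% is applied only to sampled patients, the 31% becomes 27%.

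**Simulation, DR vs R within groups.** With no PFS effect (both medians 60), the HR is 1.14 to 1.17 in non-converters and 1.01 to 1.15 in converters, nominally significant in 4 to 9% of trials. The reason shows in the non-converters: 0.1197 / 0.80 = 15% of them have an event before day 336 on R, but 0.1197 / 0.60 = 20% on DR, because DR moves more event-free patients out of that group. With a true HR of 0.50, the within-group HR is 0.56 to 0.58 in non-converters and 0.50 to 0.55 in converters.

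**Samples at progression.** The results above assume that negativity on or after progression does not count. As an extreme bound, suppose every patient with an event before day 1038 had a counted sample at that event. The ever/never HR is then 1.01, 0.85 or 0.74 at 0, 5 or 10% later conversion.

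**The case against.** The inherited method is a treatment comparison, and the neighbouring subgroup item is a DR vs R analysis, so DR vs R within each group is the ordinary reading. On that reading the distortion is small and does not favour DR. The plan specifies no hazard ratio or test of converters against non-converters, so the large figures describe a comparison that it does not name. Those below 0.62 also need assumed later conversion rates. The analysis is optional and outside the tested hierarchy (SAP 5.1.1). Conversion is limited to the treatment period, which ends at confirmed progression, so the missing rule on post-progression negativity may be settled by one cross-reference. If such samples did count, the bias could largely vanish.

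Most of this stands and sets the priority. It does not remove the point. The item names no contrast, and even the ordinary reading produces converter curves from randomisation that contain guaranteed event-free time, with nothing marking the within-group hazard ratios as non-randomised. That the bias ranges from none to large depending on whether samples at progression count is a reason to state the rule.

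The simulation omits dropout, the ±30-day marrow window and early end-of-treatment samples in patients who stop without progression. These affect the size of the bias; its direction does not depend on the exponential model.

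**Conclusion.** The concern holds, at low priority. Read literally, the analysis is a non-randomised DR vs R comparison with a small distortion (null HR 1.01 to 1.17). If converters are set against non-converters from randomisation, a null relation would appear as an HR of about 0.62 with no conversion after month 12, and 0.51 to 0.37 at an assumed 5 to 15% per later visit. These sizes rest on exponential PFS at the plan's medians, the plan's 20% / 40% conversion, conversion unrelated to PFS, and negativity on or after progression not counting. Primary MRD and main PFS inference are not affected.

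**What to change.** In SAP 5.3.2:

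1. State the intended contrast.
2. Label any DR vs R hazard ratio or curve within conversion groups as descriptive and not a randomised comparison.
3. If converters are to be compared with non-converters, replace the ever/never split with one of:
   - a Cox model with MRD conversion as a time-dependent covariate, switching at the first negative sample before progression or subsequent therapy, adjusted for treatment and stratified by cytogenetic risk; or
   - a landmark at 14 months (12 months plus the 2-month window in SAP 2.1), in patients still progression-free and uncensored, grouped by status at that time, with PFS timed from the landmark, at the final cut-off.
4. Under either method, apply the SAP 5.2.1 rule on negativity on or after progression or subsequent therapy, and do not plot ever/never curves from randomisation side by side.

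The cost is a few sentences and minor programming, with no new data. The time-dependent model has no simple Kaplan-Meier plot. The landmark drops about 24 of the 64 expected events (107 × 0.1493 + 107 × 0.0777 = 24.3) and ignores conversions first seen at 18, 24 or 36 months. It suits the final cut-off only. At the primary-analysis cut-off, with follow-up of 12 to 24 months, about 30.6 events are expected and 24.0 of them precede month 14, leaving roughly 6.5. Waiting for the 2-month window (14 to 26 months) gives 9.4 of 33.7, still few.
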